# 13. Regulatory Considerations

#### 13.1. Institutional review board/ethics committee approval

The protocol for this study has been designed in accordance with the general ethical principles outlined in the Declaration of Helsinki. The review of this protocol by the IRB/EC and the performance of all aspects of the study, including the methods used for

Page 70 of 86 Confidential

obtaining informed consent, must also be in accordance with principles enunciated in the declaration, as well as ICH Guidelines, Title 21 of the Code of Federal Regulations

(CFR), Part 50 Protection of Human Subjects and Part 56 Institutional Review Boards.

The Investigator will be responsible for preparing documents for submission to the relevant IRB/EC and obtaining written approval for this study. The approval will be obtained prior to the initiation of the study.

A copy of the IRB/EC approval for the protocol and the Informed Consent is to be provided to Celgene. The approval for both the protocol and informed consent must specify the date of approval, protocol number and version, or amendment number.

Any amendments to the protocol after receipt of IRB/EC approval must be submitted by the Investigator for review to Celgene, and then to the IRB/EC for approval. The Investigator is also responsible for notifying the IRB/EC of any serious deviations from the protocol, or anything else that may involve added risk to subjects.

Any advertisements used to recruit subjects for the study must be reviewed and approved by the IRB/EC prior to use.

#### 13.2. Informed consent

The Investigator must obtain informed consent of a subject or his/her designee prior to any study related procedures as per Good Clinical Practices (GCP) as set forth in the CFR and ICH guidelines.

Documentation that informed consent occurred prior to the subject's entry into the study and the informed consent process should be recorded in the subject's source documents.

The original consent form signed and dated by the subject and by the person consenting

Page 71 of 86 Confidential the subject prior to the subject's entry into the study, must be maintained in the

Investigator's study files.

A sample of the informed consent to be used in the study is to be forwarded to Celgene prior to submitting it to the IRB/EC for approval.

## 13.3. Subject confidentiality

Celgene affirms the subject's right to protection against invasion of privacy. In compliance with United States federal regulations, Celgene requires the Investigator to permit Celgene representatives and, when necessary, representatives of the FDA or other regulatory authorities to review and/or copy any medical records relevant to the study in accordance with local laws.

Should direct access to medical records require a waiver or authorization separate from the subject's statement of informed consent, it is the responsibility of the Investigator to obtain such permission in writing from the appropriate individual.

## 13.4. Study records requirements

The Investigator must ensure that the records and documents pertaining to the conduct of the study and the distribution of the study drug, that is copies of data collection and source documents (original documents, data, and records [e.g., hospital records; clinical and office charts; laboratory notes; memoranda; subject's diaries or evaluation checklists; pharmacy dispensing records; recorded data from automated instruments; copies or transcriptions certified after verification as being accurate copies; microfiches; photographic negatives, microfilm, or magnetic media; x-rays; subject files; and records kept at the pharmacy, at the laboratories, and at medico-technical departments involved in

Page 72 of 86 Confidential

the clinical study; documents regarding subject treatment and study drug accountability;

original signed informed consents, etc.]) be retained by the investigator for as long as

needed to comply with national and international regulations (generally 2 years after

discontinuing clinical development or after the last marketing approval). The

Investigator agrees to adhere to the document/records retention procedures by signing the

protocol.

Premature discontinuation of study

13.4.1. Single center

The responsible local clinical Investigator as well as Celgene have the right to

discontinue this study at any time for reasonable medical or administrative reasons in any

single center. Possible reasons for termination of the study could be but are not limited

to:

• Unsatisfactory enrollment with respect to quantity or quality.

• Inaccurate or incomplete data collection.

• Falsification of records.

• Failure to adhere to the study protocol.

13.4.2. Study as a whole

Any possible premature discontinuation would have to be documented adequately with

reasons being stated, and information would be issued according to local requirements

after discussions and agreement between the PI's sponsor (s) and regulatory authorities at

the institutions (e.g., IRB/EC, regulatory authorities, etc.).

# 14. Appendices

Appendix I: Classification of the plasma cell dyscrasias[22] & International Staging System (ISS)[23]

MGUS	Asymptomatic multiple myeloma	Symptomatic multiple myeloma
Serum M protein < 30g/L &	Serum M protein ≥ 30g/L or	M protein in the serum or urine
Clonal bone marrow	Clonal bone marrow	&
plasmacytosis <10%	plasmacytosis ≥ 10%	Clonal bone marrow
No other B cell	No related organ and tissue	plasmacytosis or plasmacytoma
lymphoproliferative disorder	impairment	Related organ and tissue
No related organ and tissue		impairment*
impairment		

\*Related Organ Tissue Impairment

- Hypercalcemia
- Renal dysfunction
- Anemia: hemoglobin 2 g/dL below the lower limit of normal
- Lytic bone lesions (solitary plasmacytoma requires >30% PC)
- Symptomatic hyperviscosity

Page 74 of 86 Confidential

• Amyloidosis (requires >30% PC)

Page 75 of 86

Confidential

• Recurrent bacterial infections (>2/year)

# **International Staging System[23]:**

I	$\beta 2m < 3.5 \text{ mg/dL}$
	Albumin≥3.5g/dL
II	$5.5 > \beta 2m \ge 3.5 \text{ mg/dL}$
	Or
	Albumin $<$ 3.5g/dL and $\beta$ 2m $<$ 3.5 mg/dL
III	$\beta 2m \ge 5.5 \text{ mg/dL}$

Page 76 of 86 Confidential

# Appendix II: Uniform Response Criteria as defined by the International

# **Myeloma Working Group[22]**

All relapse categories require two consecutive assessments made at anytime

before classification as relapse or disease progression and/or the institution of any new therapy.

# Measurable disease is defined as:

	• Negative immunofixation on the serum and urine, and
Complete remission	• Disapppearance of any soft tissue plasmacytomas, and
	• ≤5% plasma cells in the bone marrow (confirmation with repeat bone marrow
	is not needed)
	• CR as defined above, and
Stringent Complete	Normal free light chain (FLC) ratio, and
remission	Absence of clonal cells in the bone marrow by immunohistochemistry or
	immunofluorescence, based on a $\kappa/\lambda$ ratio of > 4:1 or < 1:2 performed on a
	minimum of 100 plasma cells (confirmation with repeat bone marrow is not
	needed)
	Serum and urine M-protein detectable by immunofixation but not on
Very Good Partial	electrophoresis, or
Remission	• 90% or greater reduction in serum M-protein plus urine M-protein level of <
	100 mg per 24 hours
D : 1D : 1	• ≥50% reduction of serum M-protein and reduction in 24-h urinary M-protein
Partial Remission	by ≥90%, or to <200mg per 24 h
	• If the serum and urine M-protein are unmeasurable*, a ≥50% decrease in the
	difference between involved and uninvolved FLC levels is required in place of
	the M-protein criteria
	• In addition to the above listed criteria, if present at baseline, a ≥50%
M 1	reduction in the size of soft tissue plasmacytomas is also required
Minimal remission	• 25-49% reduction of serum M-protein and reduction in 24-h urinary M-
	protein by \ge 50\% but less than 90\%
	• In addition to the above listed criteria, if present at baseline, a ≥25%
	reduction in the size of soft tissue plasmacytomas is also required
	Not meeting criteria for CR, VGPR, PR or progressive disease
Stable Disease	1 vot meeting effectia for Cit, v Of it, i it of progressive disease

Page 77 of 86 Confidential Increase of ≥25% from baseline in serum M-component, and the absolute **Progressive Disease** increase must be  $\geq 0.5$  g/dl. If the starting M-component is  $\geq 5$  g/dl, increases >1 g/dl are sufficient to define relapse. • Increase of ≥25% from baseline in urine M-component, and the absolute increase must be  $\geq 200 \text{ mg/}24 \text{ hours}$ • Only in patients without measurable serum and urine M-protein levels: Increase of ≥25% from baseline in the difference between involved and uninvolved FLC levels, and the absolute difference must be >10 mg/dl Increase of ≥25% from baseline in bone marrow plasma cell percentage, and the absolute % must be  $\geq 10\%$  (relapse from CR has the 5% cutoff versus 10% for other categories of relapse) • Definite development of new bone lesions or soft tissue plasmacytomas or definite increase in the size of existing bone lesions or soft tissue plasmacytomas • Development of hypercalcemia (corrected serum calcium >11.5 mg/dl or >2.65 mmol/l) that can be attributed solely to the plasma cell proliferative V. 3 12/06/2010

- Serum M-protein  $\geq 1$  g/dl ( $\geq 10$  gm/l) [10 g/l]

disorder.

- Urine M-protein  $\geq 200 \text{ mg}/24\text{h}$ 

Serum FLC assay: Involved FLC level ≥ 100 mg/dl (≥ 100 mg/l) provided serum FLC

ratio is abnormal

Page 78 of 86 **Appendix III: ECOG Performance Status Scale** Confidential

SCORE	DESCRIPTION
0	Fully active, able to carry on all pre-disease performance
	without restriction.
1	Restricted in physically strenuous activity but ambulatory and
	able to carry out work of a light or sedentary nature, e.g., light
	housework, office work.
2	Ambulatory and capable of all self-care but unable to carry
	out any work activities. Up and about more than 50% of
	waking hours.
3	Capable of only limited self-care, confined to bed or chair
	more than 50% of waking hours.
4	Completely disabled. Cannot carry on any self-care. Totally
	confined to bed or chair.
5	Dead.

Page 79 of 86 Confidential

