<sup>2 Clinical laboratory examinations include: total protein, albumin, calcium, , glucose, total bilirubin, alkaline phosphatase, AST (SGOT), ALT (SGPT), sodium, potassium, chloride, carbon dioxide, blood urea nitrogen, creatinine, and LDH.

<sup>3 Serum TSH, (Thyroid Stimulating Hormone), T3 and T4 levels every 3 months

<sup>4 Pregnancy testing for females of child bearing potential. A female of childbearing potential (a woman of childbearing potential is a sexually mature woman who: 1) has not undergone a hysterectomy or bilateral oophorectomy or 2) who has not been postmenopausal for at least 24 consecutive months [i.e., who has had menses at any time in the preceding 24 consecutive months]). Pregnancy testing must be performed 10 to 14 days and again within 24 hours prior to prescribing lenalidomide for Cycle 1. (prescriptions must be filled within 7 days). FCBP with regular or no menstruation must have a pregnancy test weekly for the first 4 weeks and then every 28 days while on therapy (including breaks in therapy); at discontinuation of lenalidomide and at Day 28 post the last dose of lenalidomide. Females with irregular menstruation must have a pregnancy test weekly for the first 4 weeks and then every 14 days while on therapy (including breaks in therapy), at discontinuation of lenalidomide and at Day 14 and Day 28 post the last dose of lenalidomide. (see Appendix VIII: Risks of Fetal Exposure, Pregnancy Testing Guidelines and Acceptable Birth Control Methods).

<sup>5 Skeletal survey is to be performed at baseline, upon addition of corticosteroids (prednisone and / or dexamethasone), discontinuation, and when clinically indicated.

Page 10 of 86 Confidential

 Bone marrow biopsy is to be performed at baseline, after 2 cycles of single agent lenalidomide therapy, to confirm CR, at the time of addition of corticosteroids (prednisone and / or dexamethasone), discontinuation, and when clinically indicated.

-  Survival follow-up to be completed every 3 months.

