## **Secondary:**

- 1- The response rate of older adults with mildly symptomatic multiple myeloma to single agent lenalidomide, lenalidomide prednisone and lenalidomide low dose dexamethasone in patients with suboptimal responses to lenalidomide monotherapy
- 2- The toxicity profile of these lenalidomide based combinations
- 3- The progression free survival of patients treated with single agent lenalidomide
- 4- The 1 year overall survival (OS) of older adults with mildly symptomatic multiple myeloma treated on this response adapted approach

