## 9.7.4.2. Bone marrow aspiration/ biopsy

At baseline, after 2 cycles of lenalidomide monotherapy, at the end of study, to confirm complete response, and as clinically indicated (see Section 2, Schedule of Study Assessments).

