## 12.2.5 Analysis on exploratory aims

The first exploratory aim is to measure a lenalidomide induced tumor specific immune response and correlate the tumor specific immune response with corticosteroid use (addition of dexamethasone or prednisone), response to therapy and duration of response. Antibody titer, measurement of tumor specific immune response, will be obtained at 4 different time points: at baseline, after 2 cycles of lenalidomide monthotherapy, at the time of addition of dexamethasone, and 2 cycles after the addition of dexamethasone.

Descriptive statistics (mean, standard deviation, median, and inter-quartile range) will be used to describe antibody titer distributions for the overall response adaptive approach and by treatment in different time points. For evaluating lenalidomide effect on immune response, the antibody titer change from baseline to after 2 cycles of lenalidomide monthotherapy will be summarized using descriptive statistics. For evaluating corticosteroid effect on immune response, the antibody titer change from baseline to either time of addition of dexamethasone or 2 cycles after the addition of dexamethasone will be summarized. These lenalidomide and corticosteroid effect will be analyzed using Version. 6 date 4/15/2016

Page 69 of 86 Confidential

either the pair t-test if the original or transformed data are normally distributed, or the Wilcoxon sign rank test whenever the normality assumption cannot be justified. The antibody titer change will also be compared between response to therapy (yes/no) using either the student's t-test or Wilcoxon rank sum test. Duration of response is defined as the time from study start to the time of disease progression on lenalidomide and dexamethasone. Cox regression model will be applied to evaluate the association between antibody titer change and duration of response.

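### Appendix II measures progression from an undefined baseline; read as study entry, it dates progression late for any patient whose value first fell

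*Combined protocol and SAP*

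**What the plan says.** **Progression.** Appendix II, under Progressive Disease, keys four criteria to a 25% rise from the same word: serum ("Increase of ≥25% from baseline in serum M-component, and the absolute" rise at least 0.5 g/dL), urine ("Increase of ≥25% from baseline in urine M-component, and the absolute" rise at least 200 mg/24 h), the free-light-chain difference, and marrow plasma cells. A relaxed limit of more than 1 g/dL is keyed to a starting M-component of at least 5 g/dL. New or larger bone lesions or plasmacytomas, and hypercalcaemia, count as progression with no reference value.

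**Marrow cutoffs.** The marrow criterion also needs an absolute percentage of at least 10%, with the note "relapse from CR has the 5% cutoff versus 10% for other categories of relapse".

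**The word elsewhere.** The schedule in section 2 heads its pre-treatment column Screening/Baseline. Section 12.2.5 lists antibody sampling "at baseline, after 2 cycles of lenalidomide monthotherapy, at the time of addition of dexamethasone, and 2 cycles after the addition of dexamethasone", so baseline is distinct from every later point. Footnote 5 of section 2 and section 9.7.4.2 use the word the same way. So does Appendix II itself, under partial remission: "In addition to the above listed criteria, if present at baseline, a ≥50"% shrinkage of plasmacytomas is required.

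**Where progression is used.** Section 12.2.1 counts PFS from the start of lenalidomide to first progression or death. The synopsis, section 5 and section 6.2 instead describe the primary endpoint as time to failure of lenalidomide plus low dose dexamethasone. A secondary endpoint is "The progression free survival of patients treated with single agent lenalidomide".

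**The concern.** Patients with a minimal response or better stay on single-agent lenalidomide until progression, so patients whose paraprotein has fallen are central to this design. If progression is measured from entry, such a patient must lose the whole response and then rise a further 25% (and at least 0.5 g/dL) before the paraprotein criterion is met. A rise that a lowest-value rule would date as an event before 12 months can then fall after 12 months, and the patient is counted as progression-free.

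Two analysts who read the word differently would date different events from the same laboratory series. Section 6.2 intends to set the result beside lenalidomide plus low dose dexamethasone, for which section 12.1 gives a 12-month PFS of about 70%, so readers need to know what the reported figure measures.

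**Working it through.** **1. The plan's own figure.** Section 12.1: 60 patients, 85% expected. 0.85 × 60 = 51. The exact binomial 95% interval for 51/60 is 73.4–92.9%, as stated. One patient is 1/60 = 1.67 points; for example, 53/60 = 88.3% (77.4–95.2%).

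**2. Thresholds.** For a reference value *r* below 5 g/dL, the serum threshold is max(1.25*r*, *r* + 0.5). The entry value of 3.0 g/dL is an assumption. As written, the threshold is max(3.75, 3.5) = 3.75 whatever the response. Delay = doubling time × log2(3.75 / lowest-value threshold), with doubling times of 2, 3 and 6 months assumed.

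| Fall from 3.0 | Lowest value | Threshold from lowest | Doublings | Delay at 2 / 3 / 6 months |
|---|---|---|---|---|
| none | 3.0 | 3.75 | 0 | 0 |
| 20% (stable disease) | 2.4 | 3.0 | 0.32 | 0.6 / 1.0 / 1.9 |
| 25% | 2.25 | 2.81 | 0.415 | 0.8 / 1.2 / 2.5 |
| 50% | 1.5 | 2.0 | 0.907 | 1.8 / 2.7 / 5.4 |
| 90% | 0.3 | 0.8 | 2.229 | 4.5 / 6.7 / 13.4 |
| to zero | 0 | 0.5 | 2.907 | 5.8 / 8.7 / 17.4 |

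The delay depends on the entry value. For a 50% fall it is 0.8 / 1.2 / 2.5 months from 0.5 g/dL (the serum eligibility floor in section 7.1.1), 1.2 / 1.8 / 3.5 from 1.0, and 2.0 / 3.0 / 6.0 from 4.0. These are continuous-time figures; actual dates fall on visits.

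**3. Effect on 12-month PFS.** Assume a constant hazard, 85% event-free under the lowest-value reference, and 30–70% of patients having a 50% fall and progressing by these criteria.

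- h = −ln(0.85)/12 = 0.01354 per month.
- As-written PFS in the affected group = exp(−h × (12 − delay)): 87.1% at 1.81 months, 88.2% at 2.72, 91.5% at 5.44.
- Gain in that group: 2.1, 3.2 and 6.5 points.
- Times 0.3 to 0.7: 0.6–1.5, 1.0–2.2 and 1.9–4.5 points overall. The full range of 0.6–4.5 points is about 0.4 to 2.7 of 60 patients.

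**4. Does the marrow criterion fit an entry reference?** From entry, the 25% rule alone requires 1.25 × entry marrow. This is already at least 10% once entry marrow is 8% or more (1.25 × 8 = 10), and at least 5% once it is 4% or more. From an entry marrow of 8% upward, neither cutoff can ever bind. A separate cutoff for relapse from CR makes more sense if the rise is measured from a value after response.

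**5. The other endpoint wording.** If the event is failure of lenalidomide plus dexamethasone, late dating of first progression still pushes failure later. But if failure is judged by the same criterion, a patient already 25% above entry when dexamethasone starts would meet it while merely stable. That dates failure early compared with a reference taken after dexamethasone began. The documents state no reference for this stage, so the net direction cannot be signed.

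**The case against.** The strongest reply is that this is an ambiguity, not a demonstrated bias. Appendix II adopts published working-group criteria and speaks of relapse from CR, so the authors may have meant a post-response reference and staff may have applied one. That stands in part: step 4 supports it, and how progression was dated in practice is not in the documents. It does not remove the point, because the only definition supplied uses a word that means study entry everywhere else, including in the same appendix.

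The size is also open to challenge. Bone, plasmacytoma and hypercalcaemia events bypass the 25% rule and shorten or abolish the delay. If patients with a fall progress less often in year one than the cohort as a whole, the shift shrinks. At a 2.7-month delay it is 1.0–2.2 points, against an interval about 19.5 points wide. All of this stands.

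A reader might infer more than the documents support:

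- *That the primary endpoint is certainly inflated.* This holds only under the entry reading and section 12.2.1; under the synopsis and sections 5 and 6.2 the direction is open.
- *That the comparison with 70% is biased.* This depends on the reference value used in the benchmark studies, which the documents do not give.
- *That a decision could flip.* Two fewer event-free patients, 49/60, gives a lower limit of 69.6%, just under 70%. But section 12.1 sizes the study for precision and sets no threshold to cross.
- *That only responders are affected.* The 20% row in the table shows otherwise.

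**Conclusion.** The point holds as a reference value left undefined whose literal reading has a known direction. Under section 12.2.1, with baseline taken as study entry, progression by paraprotein, free-light-chain or marrow criteria is dated late for any patient whose value fell, including stable disease with a partial fall. Both 12-month PFS and single-agent PFS are then shifted upward relative to a lowest-value reference, unless a reference-free form of progression comes first.

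The illustrated size is modest: at most about three patients in 60. It rests wholly on the assumed entry value, depth of fall, doubling time, affected fraction and constant hazard. The harm is a shifted and poorly defined estimate, not a changed decision rule. It is worth correcting because the remedy is small and, per the rationale for Amendment 6, the manuscript had not yet been published.

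**What to change.** In section 12.2.1, for endpoint derivation only, state that the 25% and absolute limits are measured from the lowest value since the start of lenalidomide, entry value included. Report 12-month PFS and single-agent PFS under both the as-written and the lowest-value reference. Keep the as-written result, label the other as added after accrual, and limit it to patients with serial values, stating how many lack them.

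Separately, the sponsor should reconcile baseline in Appendix II with its own relapse-from-CR cutoffs, and with the synopsis Study Design and section 6.1, where progression triggers a change of treatment. No treatment rule is proposed here. The two descriptions of the primary endpoint also need reconciling.

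The cost is a few lines of text and one added analysis, with real drawbacks:

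- The analysis is post hoc in an open-label single-arm study. Moffitt enrolment ran to 6/2013, so its 12-month outcomes matured by about 6/2014, some 22 months before the 4/15/2016 version.
- Some patients' PFS will shorten, and derived dates may differ from the dates on which treatment changed.
- Serial values from the South Korean study may be incomplete. Repeat marrow values will be sparse, since section 9.7.4.2 schedules marrow only "At baseline, after 2 cycles of lenalidomide monotherapy, at the end of study, to confirm complete response, and as clinically indicated".
- The later course of patients already taken off study may not be recoverable; they should be flagged.

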#### STUDY DESIGN:

This is a multi-center, single-arm, phase 2, open-label study of lenalidomide [Revlimid® (R)] based therapy in older adults with standard risk multiple myeloma. After enrollment patients will receive single agent lenalidomide. Responders (minimal response or better) after 2 cycles will continue present therapy until disease progression or intolerable toxicity. Patients with stable disease after 2 cycles will receive prednisone (100 mg orally on days 1 to 5 of each cycles) in addition to lenalidomide. Patients with evidence of disease progression after 2 cycles of single agent lenalidomide will receive low dose dexamethasone (40 mg weekly) in addition to lenalidomide. Patients not receiving low dose dexamethasone and with disease progression at any time during the study will be eligible to receive low dose dexamethasone in combination with lenalidomide. Patients on lenalidomide and low dose dexamethasone who experience disease progression at any time during the study will be taken off study and treated with alternative therapies..

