## STUDY ENDPOINTS

#### **Primary:**

1- The 12-month progression free survival (PFS) of older adults with mildly symptomatic multiple myeloma treated on this response adapted approach (i.e. time from lenalidomide start to failure of lenalidomide and low dose dexamethasone)

Page 6 of 86 Confidential

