## 5. Study Endpoints

## **Primary:**

1- The 12-month progression free survival (PFS) of older adults with mildly symptomatic multiple myeloma treated on this response adapted approach (i.e. time from start of lenalidomide to failure of lenalidomide and low dose dexamethasone)

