#### **12.2.** Efficacy evaluation

#### 12.2.1 Primary efficacy analysis

Progression free survival (PFS) is defined as the time from start of lenalidomide monotherapy to the first occurrence of disease progression or death on study from any cause, whichever occurs earlier. All treated patients will be included in efficacy endpoint analysis. Those patients who are treated on this trial but have not had a relevant event at the time of last follow-up will be included in the analyses of these endpoints as censored observations.

Page 66 of 86 Confidential

The primary endpoint is the point estimate of the 12-month PFS rate for the overall response adaptive approach. Number and percentage of patients who survived greater or equal to 365 days without disease progression will be summarized. The 95% confidence interval will be calculated using the exact binominal method. The PFS curves will be estimated by the Kaplan-Meier method. Median and its 95% confidence intervals will be estimated.

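### Progression is measured from study baseline with no reset when dexamethasone starts, so the progression that led to dexamethasone is not prevented from counting again as failure of lenalidomide plus dexamethasone, the primary event

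*Combined protocol and SAP*

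**What the plan says.** **Entry to Ld.** The synopsis (Study Design) gives two routes. In the first, "Patients with evidence of disease progression after 2 cycles of single agent lenalidomide will receive low dose dexamethasone". In the second, "Patients not receiving low dose dexamethasone and with disease progression at any time during the study will be eligible to receive low dose dexamethasone". Stable disease after two cycles leads to prednisone, so it is not a route into Ld. Section 6.1 agrees that dexamethasone follows progression.

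**Primary event.** Section 5 describes the endpoint as "time from start of lenalidomide to failure of lenalidomide and low dose dexamethasone". The synopsis matches it ("time from lenalidomide start to failure of lenalidomide and low dose dexamethasone"), and Section 6.2 ends the interval at the same event. Failure is not defined further. The nearest description is the synopsis sentence "Patients on lenalidomide and low dose dexamethasone who experience disease progression at any time during the study will be taken off study".

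**Progression rule.** Appendix II is the only one. Its serum criterion begins "Increase of ≥25% from baseline in serum M-component, and the absolute" and requires an absolute rise of at least 0.5 g/dl. Urine, free light chain and marrow criteria also refer to baseline. Two consecutive assessments are required. Nothing restarts the reference at a new treatment step.

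**Analysis section.** Section 12.2.1 defines PFS by "the first occurrence of disease progression or death on study from any cause".

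**Assessments at the step.** Schedule footnote 5 states: "Skeletal survey is to be performed at baseline, upon addition of corticosteroids (prednisone and / or dexamethasone), discontinuation, and when clinically indicated". Footnote 6 does the same for marrow. No section says that these results become a new reference.

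**The concern.** A patient who enters Ld on a paraprotein criterion is, on the first day of Ld, already above the threshold that defines progression. If the same threshold with the same reference is then used to decide whether Ld has failed, disease that is stable or slowly shrinking can be recorded as a failure within two assessments. The primary event would then capture a progression on the previous step, not on Ld.

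The 12-month PFS of the whole strategy is the trial's main estimate, and Section 6.2 plans to set it beside results with lenalidomide and low dose dexamethasone. An event without a stated reference also cannot be reproduced. If sites reset the reference informally, coding could differ between Moffitt and the Korean sites, and the comparison in Section 12.2.4 could read that difference as an ethnic effect. Duration of response in Section 12.2.5 also ends at progression on lenalidomide and dexamethasone and inherits the gap.

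**Working it through.** **1. The plan's own figure.** Section 12.1 gives 85% with 60 evaluable patients and a 95% interval of 73.4-92.9%. The exact binomial interval for 51/60 is 73.4-92.9%, so the figure reproduces. The sample size is not in question; the issue is which events count.

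**2. What baseline means here.** The schedule has a Screening/Baseline column covering the 28 days before treatment. Footnote 5 lists baseline and corticosteroid addition as separate times. Section 12.2.5 lists baseline and the addition of dexamethasone as separate time points. The protocol's usage therefore points to pre-treatment baseline, although Appendix II does not define the term.

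**3. Fall needed on Ld to stop meeting serum progression.** Let B be the study baseline and rB the value at the start of Ld. Both conditions must hold, so for B below 5 g/dl the threshold is T = max(1.25B, B + 0.5), and the value must fall by more than 1 - T/(rB). The two conditions coincide where 0.25B = 0.5, at B = 2 g/dl.

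| B (g/dl) | r | Ld start (g/dl) | T (g/dl) | Fall needed |
|---|---|---|---|---|
| 3.0 | 1.3 | 3.9 | 3.75 | 3.8% |
| 3.0 | 1.5 | 4.5 | 3.75 | 16.7% |
| 3.0 | 1.75 | 5.25 | 3.75 | 28.6% |
| 3.0 | 2.0 | 6.0 | 3.75 | 37.5% |
| 1.0 | 1.6 | 1.6 | 1.5 | 6.25% |

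- From 2 g/dl upward the fall needed is 1 - 1.25/r.
- Below 2 g/dl the 0.5 g/dl condition binds and the fall needed is smaller. In the last row the percentage rule alone would give 1 - 1.25/1.6 = 21.9%.
- At a starting value of 5 g/dl or more, Appendix II lets a rise above 1 g/dl suffice, so the fall needed can be larger. For B = 5.0 and r = 1.5 it is 1 - 6.0/7.5 = 20%.
- A patient who doubles and then falls 30% is at 1.4B. The rise of 0.4B reaches 0.5 g/dl only if B is at least 1.25 g/dl.

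**4. One patient under three readings.** Baseline is 3.0 g/dl, dexamethasone is added at 4.5, and the values on Ld are 4.0 and 3.9.

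- Section 12.2.1 as written: the event is the progression at 4.5, before Ld begins.
- Section 5 with study baseline as reference: 4.0/3.0 is 33% above (rise 1.0) and 3.9/3.0 is 30% above (rise 0.9). Two consecutive values qualify, so Ld has failed, although the value fell 13.3% from 4.5.
- Section 5 with the reference at the start of dexamethasone, or the lowest value after it: progression would need 1.25 x 4.5 = 5.625, or 1.25 x 3.9 = 4.875. There is no event so far.

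**5. Effect on the primary estimate.** Let m be the number of patients counted only because of the entry progression who would otherwise be progression-free at 12 months. Each costs 1/60 = 1.7 points. The documents give no value for m, so these are assumptions.

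| m | Successes | 12-month PFS | Exact 95% interval |
|---|---|---|---|
| 0 | 51/60 | 85.0% | 73.4-92.9% |
| 3 | 48/60 | 80.0% | 67.7-89.2% |
| 6 | 45/60 | 75.0% | 62.1-85.3% |
| 9 | 42/60 | 70.0% | 56.8-81.2% |

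Nine such patients would bring the planned 85% down to the roughly 70% that Section 12.1 cites for lenalidomide with low dose dexamethasone.

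**The case against.** **The intent is probably a new progression.** The synopsis speaks of patients who progress while on Ld, work-up is repeated when corticosteroids are added, and blood sampling is planned two cycles after dexamethasone. All of this assumes that patients stay on Ld. It stands as evidence of intent, but no section turns it into a reference value.

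**A reader might infer that every triggering progression automatically becomes a failure of Ld.** The documents do not support that. A patient whose value falls below the threshold is not a failure. Entry by bone lesions, plasmacytoma or hypercalcemia does not rest on a percentage change from baseline, so the arithmetic above does not apply to it.

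**Section 12.2.1 may make the question moot.** If the first progression is the event, the reference on Ld has no effect on the primary result. That is correct, but the wording contradicts the synopsis, Section 5 and Section 6.2. Once it is brought into line with them, failure of Ld still lacks a reference.

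**The net direction is not shown.** With pre-treatment baseline as reference, a responder must lose the whole response and rise 25% above the starting value before serum progression is called. That delays entry to Ld and pushes PFS upward. This stands: a reader should not infer a net downward bias in the reported rate.

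**Re-derivation is limited.** Accrual has been closed since 10/2013, and off-study follow-up is for survival, so later Ld values may not exist for patients already removed. This also stands, and it calls for a sensitivity analysis.

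**Conclusion.** The concern holds in a limited form. Under the endpoint in the synopsis, Section 5 and Section 6.2, the rule as written does not prevent the progression that led to dexamethasone from counting again as failure of Ld. This affects patients who enter Ld on a paraprotein, free light chain or marrow criterion and whose values stay above the study-baseline threshold; for serum, both the percentage and the absolute condition must still be met. It rests on reading baseline as pre-treatment, which the protocol's usage supports but Appendix II does not state.

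The size is 1.7 points for each affected patient who would otherwise be progression-free at 12 months. The total is unknown, and the drop from 85% to 80%, 75% or 70% is an illustration, not an estimate of bias. The contradiction between Section 12.2.1 and the endpoint definition is a separate defect and has to be settled at the same time. Both should be resolved before the primary result is reported.

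**What to change.** 1. In Section 12.2.1, define the primary event as failure of Ld or death from any cause, in place of the first progression, to agree with the synopsis, Section 5 and Section 6.2.
2. In Section 12.2.1 and Appendix II, define failure of Ld for analysis as Appendix II progression measured from the value at the start of dexamethasone, or the lowest value after that start. Judge bone lesions against the skeletal survey done when dexamethasone is added. Using the lowest value since study entry would not help: it would enlarge the carry-over.
3. Reconcile schedule footnotes 5 and 6, which include corticosteroid addition, with Sections 9.7.4.2 and 9.7.4.3, which omit it.
4. Re-derive recorded Ld failures from stored values and label this as post hoc. Add a sensitivity analysis for patients already taken off study who lack later Ld values, for example counting them first as failures at the recorded date and then as censored there.
5. The sponsor should reconcile the off-study wording in the synopsis with the analysis event. This point concerns the analysis definition only and proposes no clinical rule.

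The cost is a few sentences, a re-derivation and one sensitivity analysis. The schedule already places assessments at corticosteroid addition, so no new tests are needed. What cannot be recovered is later Ld data for patients removed under the literal rule.
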